8.2 Randomization and Study Drug Distribution

8.2.1.1 *Screening Number*

The subject will be assigned a screening number after signing the informed consent form. The screening number will be an 8-digit number in which the first 2 digits will signify the country, the third, fourth, and fifth digits will signify the site number in that country, and the last 3 digits will be a number assigned to subjects in the order in which they are screened. Thus, the third screened subject in the second site in the country given number 01 will have screening number 01002003. Re-screened subjects will retain their screening number and the 2 screenings will be differentiated by their screening dates. Only 1 re-screening will be allowed.

In the open-label extension, the subject will retain the same screening number.

8.2.1.2 *Randomization Number*

The randomization number will be assigned by the IWRS using the next available randomization number in the randomization code list for the subject's country.

8.2.1.3 *Randomization Procedure*

Subjects will be assigned with equal chance to 1 of the 4 treatment groups based on a randomization schedule prepared by the designated statistician. The randomization will be balanced using permuted blocks across the 4 treatment groups. The code is computer generated using the plan procedure in the SAS computer program. Validation of the randomization code is performed by quality assurance review. After finalization, the randomization code is placed in a directory with no access by the clinical study team. Once database closure has been completed, a request for unblinding is sent to the project biostatistician, at which time the code is broken and disseminated to the clinical study team for statistical analysis and clinical review.

8.2.1.4 *Drug Dispensing*

At each visit, the investigator will access the IWRS, enter his or her own user ID and PIN, and provide requested subject details (eg, subject initials and subject's date of birth). The IWRS will identify blinded blister cards and/or open label bottles of tablets to be dispensed appropriate to the phase of study.

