12.3 Analysis Data Sets

For all populations, subjects will be analyzed according to the target (randomized) dosage group including subjects who fail to achieve the target dosage during the titration phase.

Enrolled subjects: All subjects who have given informed consent to participate in this study will be considered enrolled subjects.

Intention-to-treat (ITT): All randomized subjects will be considered intention-to-treat subjects.

Modified intention-to-treat (MITT) subjects: All randomized subjects who have taken at least one dose of YKP3089 (or placebo) and have any post-baseline seizure data will be considered modified intention-to-treat subjects.

Modified intention-to-treat (MITT-M) subjects in Maintenance phase: All randomized subjects who have completed the titration phase and have taken at least one dose of YKP3089 (or placebo) in the maintenance phase and have any maintenance phase seizure data will be considered modified intention-to-treat subjects in the maintenance phase.

Per protocol population (PP): All randomized subjects who have no major protocol violations and have at least 80% drug compliance will be considered per-protocol subjects.

Safety evaluable subjects (SE): All ITT subjects.

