12.5 Primary Efficacy Analyses

12.5.1 Primary Efficacy Analysis in the United States and the Rest of the World:

The primary efficacy analysis of the primary endpoint will be based on the MITT population.

The testing strategy for the primary efficacy endpoint (percent change in seizure frequency) is to compare each of the YKP3089 dosage groups with the placebo group. Due to multiple treatment comparisons, a step-down procedure will be used to ensure the overall type I error rate is controlled at the 5% level. Each of the YKP3089 dosage groups will be compared with the placebo group according to the following hierarchy:

1. 200-mg dosage group versus placebo group
2. 400-mg dosage group versus placebo group
3. 100-mg dosage group versus placebo group

The 200-mg dosage group will be compared with the placebo group at a 2-sided 0.05 level as the first step. If no statistically significant difference is detected between the 200-mg dosage group and the placebo group, the procedure will stop and it will be concluded that none of the YKP3089 dosages are efficacious. If a statistically significant difference is detected between the 200-mg dosage group and the placebo group in favor of the 200-mg dosage group, the procedure will proceed to the next step to compare the 400-mg dosage group with the placebo group at a 2-sided 0.05 level. If a statistically significant difference is detected between the 400-mg dosage group and the placebo group in favor of the 400-mg dosage group, the procedure will proceed to the next step to compare the 100-mg dosage group with the placebo group at a 2-sided 0.05 level.

An analysis of covariance (ANCOVA) model will be fit to the ranked values of the primary efficacy endpoint. The ANCOVA will have terms for ranked baseline seizure rate and randomized treatment group. Ties will be handled using the default option in SAS

It should be noted that the primary efficacy analysis uses a non-parametric approach. Because of this, effect sizes are not estimated and tested directly, since testing is made on the rank of the primary efficacy value. However, summary tables for the actual (not the ranked) primary efficacy endpoint will be presented.

Descriptive results of the primary efficacy end point will be provided for the subjects who were titrated under the original protocol.

12.5.2 *Primary Efficacy Analyses in the countries of Europe, Australia, New Zealand, and South Africa*

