The primary efficacy analysis of the primary endpoint will be based on the MITT-M population.

The testing strategy for the primary efficacy endpoint (responder rate) is to compare each of the YKP3089 dosage groups with the placebo group. A step-down procedure will be used to ensure the type I error rate due to multiple treatment comparisons is controlled at the 5% level. Each of the YKP3089 dosage groups will be compared with the placebo group according to the following hierarchy:

1. 200-mg dosage group versus placebo group

2. 400-mg dosage group versus placebo group
3. 100-mg dosage group versus placebo group

The 200-mg dosage group will be compared with the placebo group at a 2-sided 0.05 level as the first step. If no statistically significant difference is detected between the 200-mg dosage group and the placebo group, the procedure will stop and it will be concluded that none of the YKP3089 dosages are efficacious. If a statistically significant difference is detected between the 200-mg dosage group and the placebo group in favor of the 200-mg dosage group, the procedure will proceed to the next step to compare the 400-mg dosage group with the placebo group at a 2-sided 0.05 level. If a statistically significant difference is detected between the 400-mg dosage group and the placebo group in favor of the 400-mg dosage group, the procedure will proceed to the next step to compare the 100-mg dosage group with the placebo group at a 2-sided 0.05 level.

The data will be summarized using frequencies and percents of subjects achieving at least a 50% response to treatment, the responder rate. The responder data will be analyzed using a chi-square test.

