12.6 Secondary Efficacy Analyses

12.6.1 *Secondary Efficacy Analysis in the countries of Europe, Australia, New Zealand, and South Africa*

The secondary efficacy analysis will be based on the MITT-M population.

The secondary efficacy analysis is to compare each of the YKP3089 dosage groups with the placebo group for the percent reduction in seizure frequency.

An analysis of covariance (ANCOVA) model will be fit to the ranked values of the change in seizure frequency during the maintenance phase. The ANCOVA will have terms for ranked baseline seizure rate and randomized treatment group. Ties will be handled using the default option in SAS.

It should be noted that the efficacy analysis uses a non-parametric approach. Because of this, effect sizes are not estimated and tested directly, since testing is made on the rank of the change

in seizure frequency. However, summary tables for the actual (not the ranked) change in seizure frequency will be presented.

12.6.2 *Secondary Efficacy Analysis in the United States and the Rest of the World*

The secondary efficacy analysis will be based on the MITT population

The secondary efficacy analysis is to compare each of the YKP3089 dosage groups with the placebo group for the responder rate.

The data will be summarized using frequencies and percents of subjects achieving at least a 50% response to treatment, the responder rate. The responder data will be analyzed using a chi-square test.

12.7 **Additional Secondary Efficacy Analyses**

These secondary efficacy analyses will be based on the MITT or MITT-M population

- Higher response rate of (75, 90 and 100%) of simple partial seizures with motor component plus complex partial seizures plus secondarily generalized tonic clonic seizures during the double-blind period and maintenance phase will be summarized.
- Median percent change for partial seizure subtypes (including simple partial with motor component, complex partial, and secondarily generalized tonic-clonic seizures) will be summarized.
- Seizure rate over time will be analyzed using following scheme
 - A moving average for each dose group will be computed using 4 week periods with 2 week overlap beginning from Visit 3 (V3-V5, V4-V6, V5-V6+2 weeks and so on)

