6 STUDY DESIGN AND VISIT SCHEDULE

This is a multicenter, double-blind, randomized, placebo-controlled study with an 8-week prospective baseline and an 18-week double-blind treatment period (including a 6-week titration phase and 12-week maintenance phase), followed by a 3-week blinded study drug taper period (for subjects leaving the study) or a blinded 2-week conversion period (for subjects participating in the open-label extension), with a final follow-up visit 2 weeks after the last dose of study drug.

Approximately 400 randomized subjects with partial-onset seizures will be screened at approximately 100 study sites worldwide to achieve the required sample size of 400 subjects. Study sites were classified by geographic region prior to randomization. The geographic regions defined in the study are as follows: Region 1= USA, UK, Germany, France and Australia; Region 2 = Korea and Spain; and Region 3: Remaining countries.

Subjects who have experienced at least 8 partial seizures including only simple partial seizure with motor component, complex partial seizures or secondarily generalized seizures during the baseline period without a seizure-free interval of greater than 25 days any time during those 8 weeks will be randomly assigned in a 1:1:1:1 ratio to receive placebo or YKP3089 100, 200, or 400 mg given once per day in the morning. Subjects must have at least 3 partial seizures during each of the two consecutive 4-week periods of the baseline.

Randomization was performed centrally, using an IWRS system. Randomization codes are based on a block randomization within study region.

Men and women 18 to 70 years of age, inclusive, in which subjects who meet inclusion/exclusion criteria (see study protocol) were permitted to enroll in this study.

Enrolled subjects are eligible to progress through the following study periods:

1. The Baseline/pre-treatment period consists of an 8-week prospective baseline period where pre-treatment seizure frequency information is collected. Subjects who have experienced at least 8 partial seizures during the baseline period without a seizure-free interval >25 days any time during the 8 week period may be randomized. Subjects must have at least 3 of these partial seizures during each of the two consecutive 4 week periods in

88

[figure not shown]

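### The protocol's efficacy tests leave out the region or country blocks used at randomization, so they are slightly conservative if geography predicts outcome

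*Protocol*

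**What the plan says.** **Randomization.** SAP section 6 states "Study sites were classified by geographic region prior to randomization", defines three regions by country, and adds "Randomization codes are based on a block randomization within study region". Protocol 8.2.1.2 has the IWRS assign each number "using the next available randomization number in the randomization code list for the" subject's country. Protocol 8.2.1.3 adds "The randomization will be balanced using permuted blocks across the 4 treatment groups" and names no stratification factor.

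**Analysis.** For the US and Rest of World primary endpoint (12.5.1), "The ANCOVA will have terms for ranked baseline seizure rate and randomized treatment group". The secondary analysis in 12.6.1 has the same two terms. For the responder endpoints (12.5.2 and 12.6.2), "The responder data will be analyzed using a chi-square test". Neither region nor country appears in any of these sections or in the synopsis.

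**Scope.** Protocol 12.2 leaves full detail to a SAP to be finalized before efficacy unblinding. The supplied SAP covers only the open-label extension and does no inference (11.1). Its section 6 refers to a separate double-blind SAP, which was not supplied. This point therefore concerns the protocol text.

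**The concern.** When allocation is balanced within strata, differences between strata cancel out of the treatment comparison. A test that ignores the strata still counts those differences as noise. If the strata predict outcome, its standard error is too large for the design: true type I error falls below 5%, and power is lower than the same data could give.

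The effect matters a little more here because testing is a fixed sequence. If 200 mg fails against placebo, no dose can be declared effective, and all three steps are needed to describe the effective dose range, which is the primary objective.

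The two documents also describe the blocking unit differently (country list or region block), so a reader cannot tell which factor an adjusted analysis should carry.

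**Working it through.** **1. The plan's own figure.** Protocol 12.1 gives 100 per group, a difference of 16, SD 40 and two-sided α of 0.05.

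- SE = 40 × √(2/100) = 5.657, so the standardized difference is 16/5.657 = 2.828.
- Power = Φ(2.828 − 1.96) = 80.7% (80.4% with the t distribution). The required size is 99 per group. The stated 80% reproduces.

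**2. Effect of leaving region out.** Let region explain a share R² of outcome variance, with exact balance within region, and let s = √(1 − R²). The estimate's true SE is s × 5.657, while the unadjusted test uses 5.657.

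- Size of the unadjusted test = 2 × [1 − Φ(1.96/s)]
- Unadjusted power = Φ((2.828 − 1.96)/s)
- Adjusted power = Φ(2.828/s − 1.96)
- Extra subjects the unadjusted test needs to match = [1 + 1.96(1 − s)/2.828]² − 1

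The documents give no R², so these values are assumptions:

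| R² | s | Size | Power, unadjusted | Power, adjusted | Gain (points) | Equivalent subjects |
|---|---|---|---|---|---|---|
| 0 | 1 | 5.00% | 80.7% | 80.7% | 0 | 0 |
| 2% | 0.990 | 4.77% | 80.98% | 81.52% | 0.5 | +1.4% |
| 5% | 0.975 | 4.43% | 81.35% | 82.69% | 1.3 | +3.5% |
| 10% | 0.949 | 3.88% | 82.00% | 84.65% | 2.6 | +7% |

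At R² = 20%, size would be 2.8% and power 83.4% against 88.5%.

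**3. The planned rank-ANCOVA, simulated.** With four arms, ranked baseline (assumed correlation 0.2 with outcome), regions of 40/20/40% and 20,000 runs each, power at R² of 2%, 5% and 10% is 80.2%, 80.9% and 80.9% without region, and 80.8%, 82.2% and 83.5% with it. The gains are 0.6, 1.3 and 2.6 points. A separate simulation (blocks of four, regions of 40/10/50%, baseline unrelated to outcome, 12,000 null runs) gives sizes of 4.7%, 4.5% and 3.9% without region and 4.8%, 4.9% and 5.2% with it.

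**4. Chi-square.** Assume regions of 40/20/40% and set R² to the between-region variance of the responder rate divided by p(1 − p).

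- Null rates 20/25/30%: 0.0020/0.1875 = 1.1%, size 4.9% by formula, 4.8% simulated.
- Null rates 15/25/35%: 0.0080/0.1875 = 4.3%, size 4.5% by both.
- Null rates 15/25/45%: 0.0184/0.2059 = 8.9%, size 4.0% by formula, 4.1% simulated.

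The Europe, Australia, New Zealand and South Africa responder analysis uses the MITT-M set, which admits "All randomized subjects who have completed the titration phase and have taken at least one dose" in maintenance and so loses some of the exact balance. With an assumed 15% titration dropout, the simulated sizes become 4.9%, 4.7% and 4.2%. A stratified test gains 0.1 to 3.6 power points at an assumed common odds ratio of 2.3.

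**5. The fixed sequence.** Assume a 16-point effect at every dose and a shared placebo group (pairwise correlation 0.5). The chance of passing all three steps is then 62.7%, 63.3% and 64.3% unadjusted at R² of 2%, 5% and 10%, and 63.5%, 65.4% and 68.6% adjusted.

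**6. If lists were by country.** Suppose country explains 10% of variance and region 5% of that. Adjusting for region gives Φ((2.828 − 1.96√0.95)/√0.90) = 83.3%, between 82.0% with no term and 84.6% with country. About half of the forgone power is recovered.

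**The case against.** **The double-blind SAP may already adjust.** This is fair, and it limits the finding to the protocol. But the protocol lists its model terms explicitly, so if the double-blind SAP adds region, the two need to be aligned.

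**The plan still meets its own target.** This is true. Unadjusted power is at least 80.7% in every row of the table and type I error never exceeds 5%. What is at stake is a forgone gain; the test remains valid.

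**Loss of precision is loose wording.** This is largely right. With balanced blocks, the treatment estimate varies about equally whether or not region is fitted. What suffers is the standard error used by the test, which is too large, and hence power.

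**R² is assumed.** This stands. The regions group distant countries, nothing says they predict outcome, and what counts is what region adds beyond ranked baseline. That is why a range starting at zero is shown.

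**Country and region may not conflict.** A regional list assigned to a country would fit the words of 8.2.1.2. The texts can be reconciled, but they do not reconcile themselves.

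**It may be too late.** The extension SAP is dated 2021 and describes randomization in the past tense, so efficacy data may already be unblinded. In that case only a sensitivity analysis remains open.

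**Conclusion.** The point holds, and it is small. The protocol blocks allocation by geography and then tests without it. If region explains 2% to 10% of outcome variance, true size is about 4.8% to 3.9%, and 0.5 to 2.6 power points per comparison are forgone (about 0.8 to 4.4 for the full sequence). If region is not prognostic, nothing is lost. Type I error is not inflated and the sample size stands. These figures rest on an assumed R², assumed region shares and responder rates, and near-exact balance within strata. The unclear blocking unit is a separate documentation gap whatever the value of R². The correction is worth making because it costs almost nothing; confidence is medium because the double-blind SAP is unseen.

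**What to change.** 1. Before efficacy unblinding, add the three-level region factor to the rank-ANCOVA in 12.5.1 and 12.6.1, and replace the chi-square in 12.5.2 and 12.6.2 with a Cochran-Mantel-Haenszel test stratified by region.
2. If the double-blind SAP already does this, align the protocol wording with it.
3. If efficacy data are already unblinded, keep the specified tests as primary and report the adjusted ones only as labelled sensitivity analyses.
4. Reconcile protocol 8.2.1.2 with SAP section 6 so that both name the stratum the IWRS used. Region is a valid covariate either way because the regions are groups of countries, but if lists were by country it recovers only part of the forgone power.

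The cost is wording, a few lines of code and two degrees of freedom. No extra data or subjects are needed.

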6 STUDY DESIGN

6.1 Overview

This is a multicenter, double-blind, randomized, placebo-controlled study with an 8-week prospective baseline and an 18-week double-blind treatment period (including a 6-week titration phase and 12-week maintenance phase), followed by a 3-week blinded study drug taper period (for subjects leaving the study) or a blinded 2-week conversion period (for subjects participating in the open-label extension), with a final follow-up visit 2 weeks after the last dose of study drug.

Subjects who meet all inclusion criteria and none of the exclusion criteria will first undergo an 8-week baseline to assess seizure frequency. Subjects who have experienced at least 8 seizures during the baseline period without a seizure-free interval of greater than 25 days any time during those 8 weeks will be randomly assigned in a 1:1:1:1 ratio to receive placebo or YKP3089 100, 200, or 400 mg given once per day in the morning. Subjects must have at least 3 partial seizures during each of the two consecutive 4-week periods of the baseline.

Subjects will first enter a 6-week titration phase, during which the initial dose will be 50mg/day. The planned increase in the daily dose will be 50mg/day/week increments until 200mg is reached and after which the dose will be increased by 100mg/day/week in subjects randomized to 400mg/day. Subjects will then enter a 12-week double-blind maintenance phase.

[figure not shown]
Only subjects who complete the double-blind maintenance phase will be given the option to continue treatment in an open-label extension. Those who choose not to enter the open-label extension or who withdraw prematurely will taper off the study drug.

For those subjects not entering the open-label extension, the taper period will last 3 weeks and will be followed by a final visit 14 days after the last dose of study drug.

Those subjects entering the open-label extension will enter a 2-week blinded crossover period, during which all subjects will be converted to a target dose of 300 mg once daily of open-label YKP3089.

Figure 2 provides an overview of the study design.

Figure 2. Overview of Study Design

6.1.1 *Screening and Pre-Randomization (Baseline Period)*

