6.2 Study Endpoints

The primary efficacy endpoints reflect the United States Food and Drug Administration (FDA) recommendation of percent reduction in seizure frequency for registration which is adopted by many countries in the rest of the world, and the European Agency for the Evaluation of Medicinal Products (EMA) recommendation of the responder rate for registration in Europe, which is also adopted by Australia, New Zealand, and South Africa.

6.2.1 *Primary Efficacy Endpoint in the United States and the Rest of the World*

The primary efficacy endpoint to be evaluated for registration in the United States and the Rest of the World is the percent change from the pretreatment baseline phase in seizure frequency (average monthly seizure rate per 28 days) of all simple partial motor, complex partial, or secondarily generalized seizures compared with the double-blind treatment phase.

The baseline rate (B) is calculated by counting the number of seizures over the baseline period and dividing by the number of days in the interval with non-missing seizure data and then multiplying by 28. The double-blind rate (D) is calculated in a similar manner. The percent change is equal to $100 \times (D - B) / B$. Simple partial seizures without a motor/visual component will not be counted.

This value will be undefined if $B = 0$. For the primary efficacy analysis, there will not be any baseline values with zero seizures. However, for the analysis of seizure sub-types, there is a possibility that B may be zero. In this case, B will be set to a value of 1.

6.2.2 *Primary Efficacy Endpoint in the countries of Europe, Australia, New Zealand, and South Africa*

The primary efficacy endpoint to be evaluated for registration in the countries of Europe, Australia, New Zealand, and South Africa is the responder rate defined as a 50% or greater reduction during the maintenance phase of the double blind period in the seizure frequency from baseline.

The responder endpoint is a binary indicator endpoint defined as 1 if the primary endpoint is $\leq -50\%$, and 0 otherwise

6.2.3 *Secondary Efficacy Endpoint in the countries of Europe, Australia, New Zealand, and South Africa*

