12 STATISTICAL METHODS AND PLANNED ANALYSES

12.1 Sample size estimation

A sample size of 100 subjects per treatment group will provide 80% power to detect a difference of 16% in median percent reduction in seizure frequency between an active dosage group and placebo group, at a 2-sided significance level of 0.05, assuming a standard deviation of 40%.

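### The responder tests ignore baseline seizure rate; adjusting for it is an optional refinement worth about 0 to 3 points of power

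*Protocol*

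**What the plan says.** Protocol 6.2 defines response relative to baseline. "The baseline rate (B) is calculated by counting the number of seizures over the baseline period", dividing by the days with seizure data and multiplying by 28. "The responder endpoint is a binary indicator endpoint defined as 1" when the percent change is -50% or lower. The European endpoint uses the 12-week maintenance phase; the US secondary uses the whole double-blind period.

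Sections 12.5.2 and 12.6.2 test the responder rate identically: "The responder data will be analyzed using a chi-square test". Neither names a covariate. The European comparisons run in fixed sequence: "The 200-mg dosage group will be compared with the placebo group at a 2-sided 0.05 level as the first step", then 400 mg, then 100 mg, each only if the previous step succeeds.

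For percent change, 12.5.1 says "The ANCOVA will have terms for ranked baseline seizure rate and randomized treatment group", and 12.6.1 repeats this for the European secondary analysis.

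Section 12.1 covers percent reduction only: "A sample size of 100 subjects per treatment group will provide 80% power to detect a difference of 16% in median percent reduction". No responder rate or responder power is given. The supplied SAP covers only the open-label extension, without inference, and mentions a separate double-blind SAP.

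**The concern.** Response is a fall of at least half from a baseline that is itself a noisy 8-week count. Inclusion criterion 6 keeps only subjects with at least 8 seizures in that time and at least 3 in each 4-week half. If a subject's counts vary more than Poisson, some enter with a baseline that is high by chance, regress, and meet the 50% criterion without any drug effect. Baseline rate then carries information about response that the chi-square does not use.

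Within the European plan, the secondary analysis adjusts for baseline and the primary does not, and no reason is given. The 200 mg responder test gates the other two doses, and its power is unstated, so even a small gain there would be useful.

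**Working it through.** **1. The plan's own figure.** Inputs from 12.1: 100 per arm, difference 16, SD 40, two-sided 0.05.

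Power = Φ(16 / (40 × √(2/100)) − 1.96) = Φ(2.83 − 1.96) = 80.7%. Required n = 2 × (1.96 + 0.84)² × (40/16)², or 99 per arm. The stated 80% reproduces, but it concerns percent reduction and does not bear on the responder test.

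**2. Responder power without adjustment.** The responder rates are assumptions. Allocation is equal (6.1: "will be randomly assigned in a 1:1:1:1 ratio to receive placebo or YKP3089 100", 200 or 400 mg). With n = 100,

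Power = Φ{ [(p1 − p0)√n − 1.96√(2p̄(1−p̄))] / √(p0(1−p0) + p1(1−p1)) }.

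- Scenario A, 25% v 45%: (2.000 − 1.96 × 0.6745) / 0.6595 = 1.03, so 84.8%.
- Scenario B uses protocol figures: Phase 2a placebo median 21% (4.4.4), plus 16 points, SD 40, normal distribution. p0 = 1 − Φ((50 − 21)/40) = 23.4%; p1 = 1 − Φ((50 − 37)/40) = 37.3%. Power is 56.8%.

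**3. Gain for a given association.** Let R² be the squared correlation of baseline rate with responder status. Adjustment acts roughly as if n became n/(1 − R²).

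| R² | A (from 84.8%) | B (from 56.8%) | Gain, points |
|---|---|---|---|
| 0.01 | 85.2% | 57.2% | 0.4 |
| 0.02 | 85.5% | 57.6% | 0.7–0.8 |
| 0.05 | 86.6% | 58.9% | 1.8–2.1 |
| 0.10 | 88.3% | 61.3% | 3.5–4.5 |

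**4. What R² might be.** The documents give no figure, so seizure counts were simulated with the entry rule applied. The settings are assumptions: lognormal true rates, gamma-Poisson counts, 95 per arm. Simulations 1 and 2 take a 20% rate reduction on placebo and a further 30% on drug. Simulation 1 has 6,000 replicates, median 5–9 per 28 days, log SD 0.7–0.9 and individual-response log SD 0.4–0.6. Simulation 2 has 3,000 replicates, median 7, log SD 0.8 and response log SD 0.5. Simulation 3 used both an 84-day and a 126-day window, so it also covers the 18-week US endpoint.

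| 28-day dispersion | Sim 1: chi-square → logistic | Sim 2: chi-square → logistic | Sim 3: gain, points |
|---|---|---|---|
| 0 | not run | 87.6% → 87.4% | −0.3 to −0.1 (0 to 0.1) |
| 0.1 | not run | 81.4% → 81.4% | as above |
| 0.25 | 66.4% → 67.3% | 73.6% → 75.2% | 0.7–0.8 |
| 0.5 | 62.8% → 64.0% | 62.5% → 63.9% | 1.6–1.7 |
| 1.0 | 53.3% → 56.0% | 48.6% → 49.9% | 2.3–2.5 |

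In simulation 2, R² was 0.001 at dispersion 0 and 0.1, then 0.008, 0.022 and 0.042. Placebo response in the low- and high-baseline halves was 25% v 23% at dispersion 0, and 37% v 54% at dispersion 1.0. A separate count model with dispersion 0 to 0.3 gave R² of 0.0002 to 0.013, a gain of roughly 0 to 0.6 points.

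**5. Type I error and scale.** Type I error was 4.5–5.6% for both tests across the three count simulations. In 4,000 simulated trials per setting at 25% v 43%, 100 per arm, the marginal odds ratio was 2.26. The conditional odds ratio was 2.33 at R² of about 0.03 and 2.65 at about 0.13. A standardised risk difference, which stays on the marginal scale, had type I error of 4.8–5.5%.

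**The case against.** The strongest reply is that nothing is broken. A chi-square test is valid under randomisation, and its 5% level already allows for chance baseline imbalance. That stands. A reader might infer that omitting baseline biases the result or inflates the error rate; neither the documents nor the simulations support this.

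A reader might also take the ANCOVA term as proof that baseline predicts response. It is not. The responder endpoint is already relative to baseline and then dichotomised, which may leave almost no association.

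The documents also lean, roughly, towards the low end of the range. At dispersion 1.0 the assumed model gives 42–50% placebo responders and lets 33–50% of subjects pass the seizure entry rule. Scenario B's placebo rate is about 23%, and section 7.1 plans 400 randomised from 520 screened (400/520 = 77%). These checks are loose, because screened patients are pre-selected, but they make the upper end of the gain less likely.

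Finally, 12.6.1 already gives a baseline-adjusted test in the same MITT-M population, though on the secondary endpoint, and 12.2 defers full detail to a SAP. The relevant double-blind SAP is not among the documents, so adjusted analyses may already be planned.

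**Conclusion.** The point holds as an optional improvement. Both responder tests are unadjusted as written, and the covariate is already collected and used elsewhere. Adjustment would add about 0 to 3 points of power, with type I error at about 5%. The size rests entirely on assumed rate distributions, over-dispersion and treatment effects. With nearly Poisson counts there is no gain, and at dispersion 0.25 it is about 1 to 1.5 points.

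It would be tempting to say that adjustment gains power at no cost. The documents do not support the gain as a certainty, since they give no link between baseline rate and response. Nor is it free: the odds ratio changes from marginal to conditional, and one more modelling choice must be prespecified.

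**What to change.** Before unblinding, amend 12.5.2 and 12.6.2, or the double-blind SAP if it is silent, as follows:

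- Test each dose against placebo by a likelihood-ratio test from a logistic regression of response on treatment and log baseline 28-day seizure rate. Keep the European 200, 400, 100 mg gatekeeping, and use the same order in 12.6.2.
- Report raw responder percentages and a standardised risk difference with its confidence interval beside the conditional odds ratio.
- Keep the chi-square as a sensitivity analysis.

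The cost is a few lines of text and one model statement. The covariate form must be fixed in advance, and readers must be told that the odds ratio is conditional on baseline. If efficacy data have already been unblinded, the adjusted model can serve only as a supportive analysis.
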